6.2.2 Follow-up Assessment: Immediately Post-intervention (8 weeks from baseline)

This study will not use follow-up visits. All follow-up evaluations will be performed using computer-assisted telephone interviewing (CATI). The following study outcomes will be measured within 24-48 hours from intervention completion for

intervention effects:

- Caregiver grief
- Caregiver depressive symptoms
- Caregiver anxiety symptoms
- Caregiver positive states of mind
- Caregiver conflict with facility staff
- Caregiver satisfaction with care in the facility
- Caregiver knowledge of ADRD
- Caregiver sense of loss
- Caregiver guilt
- Caregiver role captivity
- Caregiver adherence to CGMI-V/Satisfaction Survey (intervention condition)
- Changes in caregiver and care recipient status

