5.3.3 Prohibited Interventions

Participants will be excluded if already attending an ADRD caregiver chronic grief management support group.

5.4 Adherence Assessment:

We will use a Web-based tracking system, Microsoft Access, to assess the receipt of the dose consisting of eight group sessions. We will calculate attendance rates for each participant and record reasons for missing sessions. We will assess enactment of the CGMI-V intervention with specific items in an anonymous participant survey administered at 8 and 24 weeks (e.g., “Since our last assessment meeting, how often have you used: communication skills and conflict resolution techniques learned in the program when interacting with facility staff?”)

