6.2.3 Completion/Final Evaluation (24 weeks from baseline)

This study will not use a final visit. All Completion/Final evaluations will be performed using computer-assisted telephone interviewing (CATI). The following study outcomes will be measured at 24 weeks from baseline for maintenance effects:

- Caregiver grief
- Caregiver depressive symptoms
- Caregiver anxiety symptoms
- Caregiver positive states of mind
- Caregiver conflict with facility staff
- Caregiver satisfaction with care in the facility
- Caregiver knowledge of ADRD
- Caregiver sense of loss
- Caregiver guilt
- Caregiver role captivity
- Caregiver adherence to CGMI-V /Satisfaction Survey (intervention condition)
- Changes in caregiver and care recipient status

Based on our previous pilot studies²⁵⁻²⁷, we do not anticipate early termination of the CGMI-V study. We will document reasons for participant voluntary drop-out and will ask participants who may have dropped out prior to completing the 8 group-based CGMI-V sessions to participate in the 8 and 24-week follow-up assessments.

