9.2.1 Treatment Assignment Procedures

The study is a Stage I longitudinal randomized clinical trial. ADRD caregivers whose family members are in LCTFs will be recruited, screened for inclusion criteria, and randomly assigned to either CGMI-V or a Minimal Treatment (MT) control condition. Randomization will be stratified in six Waves of 24 participants each, to insure that there are exactly 12 participants in each condition. In Wave 1, we will randomly assign the first 24 enrolled participants to either the CGMI-V condition ($n = 12$; 6/group) or MT control condition ($n = 12$). The same process will continue for the next five Waves. Recruiters and data collectors will be blinded as to the random assignment of each participant. Once caregivers sign the consent to enroll in the study, the Project Director will use randomization software to assign each enrolled participant to CGMI-V or the MT condition. The Project Director will then inform the participants directly of their assignments and ask them to maintain confidentiality about their assignment at data collection points.

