10 DATA COLLECTION AND QUALITY ASSURANCE

10.1 Data Collection Forms

Trained Research Assistants (RAs) blinded to treatment condition will use Computer-assisted Telephone Interviewing (CATI) to complete all initial screening and data collection interviews. Study RAs will read each question and enter the response directly into the secure, web-based Research Electronic Data Capture (REDCap).

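### An intervention-only survey sits inside the follow-up interviews done by blinded assistants, conflicts with its description as anonymous, and can reveal allocation from week 8

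*Combined protocol and SAP*

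**What the plan says.** On blinding, section 9.2.1 states: "Recruiters and data collectors will be blinded as to the random assignment of each participant". Its one stated safeguard is that the Project Director tells participants their assignment and will "ask them to maintain confidentiality about their assignment at data collection points".

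On who collects data and how, section 10.1 states: "Trained Research Assistants (RAs) blinded to treatment condition will use Computer-assisted Telephone Interviewing (CATI) to complete all initial screening and data collection interviews". It adds: "Study RAs will read each question and enter the response directly into the secure, web-based Research Electronic Data Capture (REDCap".

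On the follow-up assessments, section 6.2.2 (week 8) states "All follow-up evaluations will be performed using computer-assisted telephone interviewing (CATI" and section 6.2.3 (week 24) states "All Completion/Final evaluations will be performed using computer-assisted telephone interviewing (CATI". The list in 6.2.2 includes "Caregiver adherence to CGMI-V/Satisfaction Survey (intervention condition", and 6.2.3 has the same entry with the same restriction to one arm. The schedule in 6.1 marks this survey at both time points, in the phone/online interview columns that also hold the outcome scales.

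On the survey itself, section 5.4 says that enactment of the intervention is assessed by items "in an anonymous participant survey administered at 8 and 24 weeks". Its example item asks how often the caregiver has used skills taught in the program since the previous assessment meeting.

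**The concern.** A survey given to one arm only identifies that arm. An RA who reads it to one caregiver and not to another has been shown both assignments, whatever the caregivers keep to themselves. The request for confidentiality in 9.2.1 offers no protection, because the disclosure comes from the interview script and not from the participant.

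This matters because the primary outcome (chronic grief) and all secondary outcomes are self-reports read aloud and entered by the RA. An interviewer who knows the arm may prompt, clarify or record differently. Participants cannot be blinded here, so interviewer blinding is the only masking of outcome measurement that the plan claims. The 24-week data enter the multilevel model over three time points in section 9.5. The resulting effect size is meant to inform whether a larger trial is warranted, and a larger sample does not remove a measurement bias that differs by arm.

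**Working it through.** The plan gives no figure on this point, so the check compares sections and then counts who could be affected.

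**Step 1: how the survey is given.** Two readings are possible.

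| | Reading A: RA-read | Reading B: separate anonymous form |
|---|---|---|
| Support | 6.1 (interview columns), 6.2.2 and 6.2.3 (all by CATI), 10.1 (RAs complete all interviews) | 5.4 (anonymous), 9.2.1 and 10.1 (data collectors blinded) |
| What it contradicts | Anonymity in 5.4; blinding in 9.2.1 and 10.1 | Placement in 6.1, 6.2.2 and 6.2.3 |
| Does it reveal allocation? | Yes | Not by this route |

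Neither reading fits every section. An interview read aloud to an identified caregiver and keyed by the interviewer is not anonymous to that interviewer. Conversely, 5.4 names no self-completed form, separate link or unblinded administrator.

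**Step 2: week-8 outcomes under reading A.** In both lists the survey comes after ten measures: grief, depressive symptoms, anxiety, positive states of mind, conflict with staff, satisfaction with care, knowledge, loss, guilt and role captivity. If the call follows that order, all ten are recorded before the survey reveals anything. Only the change-in-status items come later. The protocol text does not make the order binding.

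**Step 3: week-24 outcomes under reading A.** The week-24 scales are collected with known allocation if at least one of these is true:

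- the RA who made the week-8 call also makes the week-24 call; or
- the week-24 RA can see the week-8 record or an arm-specific form.

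The protocol text neither states nor excludes either condition.

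**Step 4: how many participants.** Section 9.2 plans 72 per arm, from 64 per arm with 10% attrition: 64 / 0.90 = 71.1, rounded up to 72.

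- Upper limit with no attrition: 72 identified by being asked + 72 identified by not being asked = 144.
- At the planned attrition: 64 + 64 = 128.
- Lower limit for 24-week outcomes: 0, under reading B, or under reading A with a different RA who has no access to week-8 forms.

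**The case against.** The strongest reply is that 5.4 is the one section describing how enactment is assessed, and it calls the survey anonymous. Together with the blinding statements, this suggests a form kept apart from the RA interview. The lists in 6.2.2 and 6.2.3 are loosely drawn: they are introduced as study outcomes but include a satisfaction survey and a status update. The RA manual (Appendix C) is not part of the text reviewed and may settle who gives the survey. This stands to the extent that the mode of administration is contradictory, not established. It does not remove the need to reconcile the sections, since following 6.2.2, 6.2.3 and 10.1 as written would break the blind.

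A reader might go further and infer that interviewers will learn every participant's allocation, that week-8 outcomes are compromised, or that all 24-week interviews are unblinded. The documents support none of these as fact. The first takes reading A as settled. The second runs against the listed order. The third needs RA continuity or access to records that the plan does not describe.

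It is also fair to say that the outcomes use fixed response options and that participants already know their arm, so expectation effects exist whatever the RA knows. The added effect of interviewer knowledge may be modest, and the documents give no basis for putting a size on it. That limits the likely harm, but the plan still claims a protection that its own procedures can undo.

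**Conclusion.** The concern holds as an internal conflict with a possible consequence for blinding. Sections 6.1, 6.2.2 and 6.2.3 place a one-arm survey inside interviews that 10.1 assigns to blinded RAs, while 5.4 calls the same survey anonymous. If 6.2.2, 6.2.3 and 10.1 are followed, RAs can learn allocation from week 8.

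The size is conditional. Week-8 outcomes are probably unaffected, assuming the listed order is kept. Week-24 outcomes are exposed if the same RA makes both calls or can see week-8 arm-specific forms; this could involve anywhere from 0 to about 128 participants at the planned attrition. No bias in the grief effect size can be calculated from the documents. The point concerns interviewer blinding only and does not invalidate the trial, but it should be corrected because the correction is cheap.

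**What to change.** 1. Remove the survey from the RA-administered battery in 6.1, 6.2.2 and 6.2.3.
2. Give it to the CGMI-V arm as a separate self-completed form, either an anonymous REDCap link or paper, in line with 5.4. It should be sent by unblinded staff after the outcome interview is complete. The Project Director already knows the assignments under 9.2.1 and could do this.
3. State in 10.1 that RAs neither administer nor see the survey or any other arm-specific form, at week 8 or week 24.
4. State the mode and the sender in 5.4, so that all five sections agree.

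The change requires protocol wording and one form or link. It needs no extra staff and leaves the sample size, endpoints and analysis as they are. The cost is a somewhat lower response rate to the survey. Because the form stays anonymous, answers could not be linked to individual outcomes, but 5.4 already accepts that. Session attendance is tracked separately for each participant and is unaffected.

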6.2.3 Completion/Final Evaluation (24 weeks from baseline)

This study will not use a final visit. All Completion/Final evaluations will be performed using computer-assisted telephone interviewing (CATI). The following study outcomes will be measured at 24 weeks from baseline for maintenance effects:

- Caregiver grief
- Caregiver depressive symptoms
- Caregiver anxiety symptoms
- Caregiver positive states of mind
- Caregiver conflict with facility staff
- Caregiver satisfaction with care in the facility
- Caregiver knowledge of ADRD
- Caregiver sense of loss
- Caregiver guilt
- Caregiver role captivity
- Caregiver adherence to CGMI-V /Satisfaction Survey (intervention condition)
- Changes in caregiver and care recipient status

Based on our previous pilot studies²⁵⁻²⁷, we do not anticipate early termination of the CGMI-V study. We will document reasons for participant voluntary drop-out and will ask participants who may have dropped out prior to completing the 8 group-based CGMI-V sessions to participate in the 8 and 24-week follow-up assessments.

7 SAFETY ASSESSMENTS

Participant safety will be monitored once each individual is screened and enrolled in the study. CGMI-V is a low risk behavioral intervention designed to support ADRD

caregivers emotionally in the context of placement of a family member with ADRD in a long-term care facility. The proposed intervention poses minimal risk to participants.

During screening and data collection for both conditions, there is potential risk for caregivers to disclose:

- Depressive symptoms (high levels indicative of clinical depression)
- Suicidal ideation

During the Chronic Grief Management Intervention-Video (CGMI-V) intervention implementation, emotional upset may occur especially during the last four sessions, when grief processing becomes the focus of the intervention. Caregivers may disclose high levels of:

- Depressive symptoms (high levels indicative of clinical depression)
- Suicidal ideation

7.1 Specification of Safety Parameters

- A score greater than 16 points (indicative of risk for clinical depression) on the Center for Epidemiological Studies-Depression Scale (CES-D)⁴⁰
- A score >1 on the PHQ 9 suicidal assessment item: “Thoughts that you would be better off dead or of hurting yourself”
- Verbalizing suicidal ideation during CGMI-V group session intervention implementation

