Control condition. Caregivers in the control condition will receive Minimal Treatment (MT) consisting of written information about late-stage ADRD (Alzheimer's Association) at baseline. The Project Director will mail caregivers in the MT control condition all written information materials.

4 **SELECTION AND ENROLLMENT OF PARTICIPANTS**

We will recruit a sample of 144 ADRD caregivers who have a family member residing in dementia care or memory care units in long-term care facilities located in the Chicago metropolitan area. We have well-established collaborating relationships with 35 long-term care facilities that will give us access to a diverse pool of approximately 1,000 ADRD family caregivers.

4.1 **Inclusion Criteria**

Participants must meet all inclusion criteria listed below in order to participate in this study.

- 21 years of age or older
- Identified as family member, fictive kin (self-identified family member) or partner of care recipient at any time post permanent placement of care in LTCF
- Care recipient has a documented ADRD diagnosis and resides in any type of unit in a long-term care facility
- Possessing self-reported basic computer literacy and in-home internet access
- Able to speak, read, and write English
- Not currently attending another ADRD caregiver grief management group

- Experiencing high to moderate levels of grief per screening with the Marwit-Meuser Caregiver Grief Inventory-Short Form (scores 25 or above), and/or experiencing high levels of depressive symptoms per screening with PHQ9 (scores 10 or above)
- Caregivers whose care recipients die during the course of the intervention will remain in the study

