4.2 Exclusion Criteria

All candidates meeting any of the exclusion criteria listed below will be excluded from study participation.

- Younger than 21 years of age
- Care recipient does not have a documented diagnosis of ADRD;
- Self-reports a lack of basic computer skills and no internet access.
- Unable to speak, read, and write English
- Currently attending an ADRD caregiver grief management group
- Experiencing low levels of grief per screening with the Marwit-Meuser Caregiver Grief Inventory-Short Form (scores below 25), and/or experiencing low levels of depressive symptoms per screening with PHQ9 (scores below 10)

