7.2 Methods and Timing for Assessing, Recording, and Analyzing Safety Parameters

CGMI-V is a low risk behavioral intervention designed to support ADRD caregivers emotionally within the first two years of placement of a family member with ADRD in a long-term care facility. The proposed intervention poses minimal risk to participants.

Identified safety parameters identified above in 7.1 will be assessed at: pre-enrollment screening, and the three data collection points (baseline and 8 and 24-weeks).

Interventionists will implement suicide protocol in the event of reported suicidal ideation during group sessions.

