7.3 Adverse Events and Serious Adverse Events

An **adverse event (AE)** is generally defined as any unfavorable and unintended diagnosis, symptom, sign (including an abnormal laboratory finding), syndrome or disease which either occurs during the study, having been absent at baseline, or if present at baseline, appears to worsen. An example of an Adverse Event (AE) anticipated for this study would be, during data collection, a Center for Epidemiological Studies-Depression Scale (CES-D) score greater than 16 points, indicative of risk for clinical depression. Whether or not this high

score is associated with study participation, we will monitor and report it as an AE, per protocol.

A **serious adverse event (SAE)** is generally defined as any untoward medical occurrence that results in death, is life threatening, requires inpatient hospitalization or prolongation of existing hospitalization, results in persistent or significant disability/incapacity, or is a congenital anomaly. An example of a Serious Adverse Event (SAE) anticipated for this study would be a participant's endorsement of suicidal ideation when screened with the PHQ-9 or disclosing suicidal ideation in a group session. Whether or not associated with study participation, we will monitor and report suicidal ideation or intention as a SAE, per protocol adopted from the Office of the Human Research Protection Program's *Research Protocols and Risk of Suicide Guidelines* (2012).

An Unanticipated Problem (UP) for this study would be any study participant incident, experience or outcomes that are unexpected in severity or frequency suggesting that participants are at greater risk of harm than anticipated. An example of an Unanticipated Problem (UP) for this study would be a participant becoming extremely upset with intervention content, to the point of dropping off from the study as a consequence. Whether or not associated with study participation, we will monitor and report per protocol.

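### The PHQ-9 suicidal-item safety parameter in 7.1 starts above 1, while 7.3 makes endorsement of ideation an SAE with no score cut, so an item score of exactly 1 gets two answers

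*Combined protocol and SAP*

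**What the plan says.** Section 7.1 names three safety parameters: a CES-D score above 16, "A score >1 on the PHQ 9 suicidal assessment item", and suicidal ideation voiced in a group session. It attaches no action to any of them.

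Section 7.2 gives the timing: "Identified safety parameters identified above in 7.1 will be assessed at: pre-enrollment screening, and the three data collection points". It adds: "Interventionists will implement suicide protocol in the event of reported suicidal ideation during group sessions".

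Section 7.3 classifies events. Its AE example restates the depression threshold from 7.1: "Center for Epidemiological Studies-Depression Scale (CES-D) score greater than 16 points". Its SAE example is a participant's "endorsement of suicidal ideation when screened with the PHQ-9", or disclosure in a group session. The commitment that follows is unqualified: "we will monitor and report suicidal ideation or intention as a SAE, per protocol adopted from the Office of the Human Research Protection". No PHQ-9 item score appears in 7.3, and nothing there refers back to the cut in 7.1. The plan does not define endorsement or print the response coding of the item.

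Elsewhere the PHQ-9 appears only as a screening instrument with a total-score cut. Section 4.1 (repeated in 6.2.1) admits caregivers "experiencing high levels of depressive symptoms per screening with PHQ9 (scores 10 or above"), as an alternative or addition to a grief score. Section 4.2 uses the complement, "experiencing low levels of depressive symptoms per screening with PHQ9 (scores below 10").

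**The concern.** Whoever scores the item needs one rule for when an answer is a safety finding. The text offers two. Under 7.1 the finding begins above 1. Under 7.3 any endorsement of ideation counts. The lowest positive answer falls between them.

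This matters most at screening. Section 7 itself expects that ideation may be disclosed then. By the schedule in 6.1, the PHQ-9 item is also the only parameter in 7.1 that is available at that contact. If staff work from 7.1, a positive answer to a question about being better off dead or hurting oneself would not meet the listed parameter, although 7.3 promises to report it.

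**Working it through.** There is no design figure to reproduce. The check compares the two rules at each item score and then asks at which contacts the comparison applies.

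**Step 1: coding.** The documents do not print the item coding, so it has to be assumed. The total-score cut of 10 (4.1, 4.2) helps to choose.
- Coded from 1: the minimum total is 9 × 1 = 9. The only total below 10 would be 9, so a total one point above the floor would already count as a high level of symptoms.
- Coded from 0: the minimum total is 9 × 0 = 0, and totals 0 to 9 fall below the cut.

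Coding from 0 is the sensible reading, but it remains an inference.

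**Step 2: the two rules side by side**, taking endorsement to mean any answer above the lowest.

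| Coding | Item score | Meets 7.1 (>1) | Meets wording of 7.3 |
|---|---|---|---|
| from 0 | 0 | no | no |
| from 0 | 1 | **no** | **yes** |
| from 0 | 2 or more | yes | yes |
| from 1 | 1 (lowest answer) | no | no |
| from 1 | 2 or more | yes | yes |

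With coding from 0 the rules differ at exactly one value, 1. With coding from 1 they agree throughout.

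**Step 3: contacts.**
- The PHQ-9 is explicitly given at 1 contact, screening (4.1, 4.2, 6.2.1).
- Read literally, 7.2 adds baseline, 8 and 24 weeks: 1 + 3 = 4 contacts.
- The schedule in 6.1 has 17 rows and none names the PHQ-9. Depressive symptoms are marked at baseline, 8 and 24 weeks only, and 9.4.2 measures them with the CES-D.

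The mismatch is therefore clear at 1 contact and conditional at 3 more.

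**Step 4: parameters available at screening, by the schedule.** Of the 3 in 7.1, the CES-D starts at baseline and one needs a group session: 3 − 1 − 1 = 1, the PHQ-9 item.

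**The case against.** The best reply is that 7.1 specifies and 7.3 classifies. The examples in 7.3 follow the list in 7.1, an example need not repeat every threshold, and endorsement could simply mean a score above 1. That reading is possible. Against it, 7.3 restates the CES-D cut and leaves this one out, and its reporting sentence covers ideation without qualification. If endorsement is meant to start above 1, the plan does not say so.

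A related reply is that the item is compound, so its lowest positive answer need not be ideation, and a higher cut could be deliberate. That may be so, but 7.3 draws no such distinction.

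A third reply is that nothing visible is lost. Section 7.1 triggers no action, 7.3 already promises the SAE report, and training under 10.3.1 covers participants who indicate suicide risk without naming a cut. Much of this stands. The suicide protocol, the guideline cited in 7.3 and the research assistant manual (Appendix C) are not shown, and any of them may already deal with a score of 1. Even so, 7.1 and 7.3 should agree with whatever they say.

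Finally, aligning the text the other way, by defining endorsement in 7.3 as a score above 1, would also remove the inconsistency. It would do so by narrowing a commitment that the plan now makes without limit.

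**Conclusion.** The inconsistency holds, and it is small: one item value, clear at screening and conditional at the three later assessments. It rests on two assumptions: coding from 0, which the total cut of 10 strongly implies, and reading endorsement as any positive answer. If the lowest answer is coded 1, the inconsistency disappears.

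A reader might infer more than the documents support:
- *That suicidal caregivers will be missed.* The documents give no basis for how many would score 1, and the operational protocols are not shown. No missed cases are claimed.
- *That the 72 control caregivers (144 − 72) are especially exposed because they have no group sessions.* Nobody has been randomised at screening, the one contact where the mismatch is clear. Afterwards the point matters only if the item is asked again.
- *That the cut lets at-risk caregivers into the trial.* None of the six exclusion criteria in 4.2 concerns suicidal ideation, so the item cut does not decide enrolment at any score.
- *That the mismatch applies at all four contacts.* Section 7.2 says so, but 6.1 does not show it.

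This is a minor correction to a safety trigger. It is still worth making, because the stated parameter leaves out a positive answer to a suicidality question that the reporting section appears to include. Sample size, eligibility and the primary analysis are unaffected.

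**What to change.** Change the parameter in 7.1 to *a score of 1 or more (items coded 0 upward) on the PHQ-9 suicidal assessment item*. In 7.3, define endorsement by the same cut, and carry it into the research assistants' safety protocol. If 7.2 is to be followed, add the item as a row in 6.1 at baseline, 8 and 24 weeks.

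The cost is one line in 7.1, a matching phrase in 7.3 and in the safety protocol, and possibly one row in 6.1. In operation it means some additional safety flags and follow-ups. It should add few or no SAE reports beyond those already promised, since the wording of 7.3 covers a score of 1.
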